5.3.2.4. Acceptability and Palatability of the JNJ-53718678 formulation

For the individual categories, the proportion (number [n] and percentage [%]) of ITT-i subjects with data available at Day 8 will be presented, as frequency tabulation, by treatment group. Additionally, 95% 2-sided confidence interval for each binomial proportion within the individual categories will be presented as based on the Wilson score test.

As more than one response can be selected by the caregiver, subjects will be counted in each selected response such that the sum of percentages can be >100%.

Similar presentation based on the binary categorization will be provided.

The aforementioned will be presented overall by treatment group and by the subgroups as defined in Section 2.4.

5.3.2.5. Medical Resource Utilization

The proportion (number [n] and percentage [%] based on ITT-i analysis set) of subjects with any medical care encounters (Yes vs No) will be presented, as frequency tabulation, by treatment group. Additionally, 95% 2-sided confidence interval for each binomial proportion within the individual categories will be presented as based on the Wilson score test.

Based on the binary categorization, the difference in proportion of subjects with any medical care encounters (Yes) between each active treatment group as compared to placebo will be investigated. Frequency procedure in SAS® provides Newcombe confidence limits with Mantel-Haenszel weights for the common risk difference, controlling for the two randomization stratification factors (separately). The difference in proportion of 'Yes' for any medical care encounters and both 80% and 95% 2-sided confidence intervals for this point estimate, controlling for randomization stratification factors, will be presented.

Based on those subjects with medical care encounters, the following will be presented descriptively only:

- Reason for medical care encounters
- Type of medical care encounters
- Frequency of medical care encounters

- Type of practitioner

As subjects may have experienced one or more medical care encounters, subjects will be counted in each selected category such that the sum of percentages can be >100%.

The aforementioned will be presented overall by treatment group and by the subgroups as defined in Section 2.4.

5.4. Exploratory Endpoints

Section 2.1.2 Endpoints of protocol, Amendment #6 (dated 01 December 2020), includes a detailed overview of efficacy and other endpoints (primary, secondary and exploratory) as planned per protocol. The exploratory efficacy endpoints listed below are additionally included, based on previous IAs with new information becoming available during the course of the study. These additional exploratory efficacy endpoints support decision-making for further development of JNJ-53718678 and interactions with health authorities.

Unless otherwise specified, the additional exploratory efficacy endpoints listed below, **will be analyzed and presented primarily for those subjects with symptom onset ≤ 3 days before randomization.**

Parent/Caregiver PRESORS ObsRO

- In hospitalized subjects (Cohort 1): RSV Recovery Scale (RRS): Day 1 to Day 8
- Time (hours) to resolution of RSV symptoms (concepts) and four summary parameters (ObsRO): ‘supplemental-free’ definition (*at least 24h oxygen- and hydration/feeding supplementation free*)

Note: aforementioned time (hours) to resolution (‘supplemental free’ definition) for both RSV concepts and summary parameters, developed during the course of the study based on new information available, is considered the primary definition of time (hours) to resolution for subsequent analyses. The addition of ‘at least 24h supplementation free’ requirement is to ensure that evaluation of time (hours) to resolution is an accurate reflection of the actual subject’s resolution status rather than a time (hours) confounded by possible continued use of supplementation.

- Potential association between the time (hours) to resolution of key- and overall RSV summary parameters (ObsRO [‘supplemental-free’ definition]) and covariates and/or baseline indicators of interest
- Time (hours) to resolution of key- and overall RSV summary parameters from hospital discharge (ObsRO): ‘supplemental-free’ definition (*at least 24h oxygen- and hydration/feeding supplementation free*)
- Resolved status per timepoint:
 - Day 1 to Day 8
 - BEFORE (last PRESORS ObsRO BEFORE)/AFTER (first PRESORS ObsRO AFTER) hospital discharge
- Sustained resolution of key- and overall RSV summary parameters
- AUC from immediately prior to first dose of study drug (baseline) through Day X (AUC_{Day X}), Day 8 (AUC_{Day 8}) and Day 10 (AUC_{Day 10}): key RSV symptoms

- Where Day X is defined as the day when at least 50% of Cohort 1 subjects, across all treatment groups, have been discharged from hospital.

Clinician PRESORS ClinRO

- In hospitalized subjects (Cohort 1): **clinically resolved** status (as composite endpoint): Day 1 to Day 8
- Resolved status per timepoint:
 - Day 1 to Day 8
 - BEFORE (last PRESORS ClinRO BEFORE)/AFTER (first PRESORS ClinRO AFTER) hospital discharge
- In hospitalized subjects (Cohort 1): time (hours) to resolution of the key RSV summary parameter (ClinRO): ‘supplemental-free’ definition (*at least 12h oxygen- and hydration/feeding supplementation free*)
- AUC from immediately prior to first dose of study drug (baseline) through Day X (AUC_{Day X}) and Day 8 (AUC_{Day 8}): key RSV symptoms

5.4.1. Definition

Relevant definitions and derivations pertaining to the aforementioned exploratory endpoints are specified in [Table 22](#) below.

Table 22: Exploratory Parameters

Measurement	Formula																		
PARENT/CAREGIVER PRESORS: ObsRO																			
RSV Recovery Scale (RRS): Day 1 to Day 8 [ordinal]	
In hospitalized subjects: COHORT 1: Study Day 1 to Day 8: RRS is an ordinal scale assessing a subject’s clinical status. Each category is based on data collected rather than asking the investigator to select the relevant category per subject, on each study day of assessment.
 
RRS provides 7 mutually exclusive conditions ordered from ‘best to worst’, and the analysis score reflects the subject’s worst situation on the study day of assessment: Day 1 to Day 8:
 
  
 RSV Recovery Scale (RRS)	
 
 Order	STATUS	
   
 1	Home Without Symptoms*	
 
 2	Home With Symptoms*	
 
 3	Ward, Not Requiring Supplementation (Feeding/Hydration and/or Oxygen Supplementation)	
 
 4	Ward, Requiring Supplementation(Feeding/Hydration and/or Oxygen Supplementation)	
 
 5	ICU, Not Requiring Mechanical Ventilation**	
 
 6	Requiring Mechanical Ventilation**	
 
 7	Death	
  
 
*With or without symptoms is based on the key RSV symptoms (concepts): ObsRO and assessed as:
 
 • Resolved: if ALL key RSV symptoms (concepts) scored as 0 (none) or 1 (mild) on study day of assessment OR 	RSV Recovery Scale (RRS)		Order	STATUS	1	Home Without Symptoms*	2	Home With Symptoms*	3	Ward, Not Requiring Supplementation (Feeding/Hydration and/or Oxygen Supplementation)	4	Ward, Requiring Supplementation(Feeding/Hydration and/or Oxygen Supplementation)	5	ICU, Not Requiring Mechanical Ventilation**	6	Requiring Mechanical Ventilation**	7	Death
RSV Recovery Scale (RRS)																			
Order	STATUS																		
1	Home Without Symptoms*																		
2	Home With Symptoms*																		
3	Ward, Not Requiring Supplementation (Feeding/Hydration and/or Oxygen Supplementation)																		
4	Ward, Requiring Supplementation(Feeding/Hydration and/or Oxygen Supplementation)																		
5	ICU, Not Requiring Mechanical Ventilation**																		
6	Requiring Mechanical Ventilation**																		
7	Death																		

Measurement	Formula
	
 • Not resolved: if ANY of the key RSV symptoms (concepts) scored >1 on study day of assessment Where the worst (highest) assessment collected per study day is considered. **Mechanical ventilation includes both invasive and non-invasive mechanical ventilation. 
RSV Recovery Scale: Definitions
 
Note: hospital discharge status as based on investigator evaluation captured in the Inpatient/Outpatient Status- and/or Hospitalization [Inpatient] eCRFs
 
1. Home without symptoms:
 
 • Discharged from hospital prior to study day of assessment AND • Without symptoms: based on the key RSV symptoms (concepts): ObsRO on study day of assessment 
2. Home with symptoms
 
 • Discharged from hospital prior to study day of assessment AND • With symptoms: based on the key RSV symptoms (concepts): ObsRO on study day of assessment 
3. Ward, not requiring supplementation (feeding/hydration and/or oxygen supplementation)
 
 • In non-ICU (ward) on study day of assessment (including re-hospitalization as captured in Medical Encounters [Inpatient/Outpatient] eCRF) and neither supplemental oxygen nor supplemental hydration/feeding is required by subject 
4. Ward), requiring supplementation (feeding/hydration and/or oxygen supplementation)
 
 • In ward on study day of assessment (including re-hospitalization as captured in Medical Encounters [Inpatient/Outpatient] eCRF) and supplemental oxygen and/or supplemental hydration/feeding is required by subject 
5. ICU, not requiring mechanical ventilation
 
 • ICU level of care is required at any time during the study day of assessment AND • Invasive or non-invasive mechanical ventilation not required by subject on study day of assessment 
6. Requiring mechanical ventilation
 
 • Any invasive or non-invasive mechanical ventilation on study day of assessment 
7. Death
 
 • Subject died prior to- or on study day of assessment (all-cause mortality) 
RSV Recovery Scale: ObsRO Imputation
 
In case of missing ObsRO assessments following hospital discharge, the worst-case scenario of the two home categories of the RRS will be selected, i.e. 'Home with Symptoms' and imputed as subject's assessment of RRS for that study day.

Time (hours) to resolution of RSV [summary]	Four summary parameters: 
 • Key RSV symptoms • Respiratory symptoms

Measurement	Formula

parameter]: 24h supplementation free definition [time to event]
	
 General illness behavior Overall RSV symptoms 
In the subset of hospitalized subjects (Cohort 1), time (hours) from first dose of study drug until the date/time of first observed resolution of all individual RSV concepts comprising the relevant summary parameters (refer to Attachment 2 for concepts comprising each RSV summary parameter). Where resolution occurs when ALL criteria, noted below, are met:
 
 All individual RSV concepts comprising relevant summary parameter are scored as 0 (none) or 1 (mild) for approximately 24h AND At least 24h oxygen supplementation free AND At least 24h hydration/feeding supplementation free) 
If caregiver is completing the ObsRO as expected per protocol, the approximate 24h summary score resolution can be defined with the considerations as detailed in Section 5.3.1.2.1.
 
In case not all RSV concepts, comprising a summary parameter, are resolved, data will be censored. Similar rules as for time to resolution of each ObsRO individual symptom (concept) will be applied as described in Section 5.3.1.2.1, such that:
 
time to event (hours) = (date/time of event or censoring – date/time of first dose of study drug)/3600, rounded to one decimal


Time (hours) to resolution of RSV [summary parameter] from hospital discharge [time to event]
	
RSV summary parameters:
 
 Key RSV symptoms Overall RSV symptoms 
In the subset of hospitalized subjects (Cohort 1) ‘not resolved’ at date/time of hospital discharge as based on parent/caregiver PRESORS ObsRO: Time (hours) from hospital discharge until the date/time of first observed resolution of all individual RSV concepts comprising the relevant summary parameter (refer to Attachment 2 for concepts comprising each RSV summary parameter). Where resolution is defined as a score of 0 (none) or 1 (mild) for approximately 24h.
 
Utilizing the same derived variables as detailed in Section 5.3.1.2.1:
 
 Time (hours) to resolution Time (hours) to hospital discharge 
time to event (hours) = max(time to resolution [as defined above]) – time to hospital discharge), rounded to one decimal
 
For those subjects ‘resolved’ at date/time of hospital discharge, time (hours) is set to 0h.

Measurement	Formula
Resolved status as based on PRESORS ObsRO: Day 1 to Day 8 [concepts]	
For ObsRO symptoms (concepts): sleep disturbance, crying, illness behavior, breathing problems, retractions, tachypnea, breathing sounds, cough, nasal secretions, tachycardia, feeding, dehydration:
 
Day 1 to Day 8: Resolved status per study day will be categorized as:
 
 • RESOLVED: if individual RSV concept is scored as 0 (none) or 1 (mild) • NOT RESOLVED: if individual RSV concept is scored >1 • MISSING: if no ObsRO assessment for given day (no imputation) 
Note: resolved status will be derived for each study day to Day 21, considering the worst (highest) assessment collected per study day, but is only presented from Day 1 to Day 8.

Resolved status BEFORE/ AFTER HOSPITAL DISCHARGE as based on PRESORS ObsRO [concepts]	
Hospital Discharge: In the subset of hospitalized subjects at time of hospital discharge: for each ObsRO concept, resolved status of the last ObsRO assessment BEFORE hospital discharge/first ObsRO assessment AFTER hospital discharge, will be categorized as described above.

Resolved status as based on PRESORS ObsRO: Day 1 to Day 8 [summary parameters]	
RSV summary parameters:
 
 • Key RSV symptoms • Overall RSV symptoms 
Day 1 to Day 8: Resolved status per study day will be categorized as:
 
 • RESOLVED: if individual RSV concepts comprising the relevant summary parameter are all scored as 0 (none) or 1 (mild) • NOT RESOLVED: if any of the individual RSV concepts comprising the relevant summary parameter are scored >1 • MISSING: if no ObsRO assessment for given day (no imputation) 
Note: resolved status will be derived for each study day to Day 21, considering the worst (highest) assessment collected per study day, but is only presented from Day 1 to Day 8.

Resolved status BEFORE/ AFTER HOSPITAL DISCHARGE as based on PRESORS ObsRO [summary parameters]	
RSV summary parameters:
 
 • Key RSV symptoms • Overall RSV symptoms 
Hospital Discharge: In hospitalized subjects at time of hospital discharge: for RSV summary parameters, resolved status of the last ObsRO assessment BEFORE hospital discharge/first ObsRO assessment AFTER hospital discharge, will be categorized as described above.

Measurement	Formula
Sustained resolution of RSV [summary parameter] [categorical]	
RSV summary parameters:
 
 • Key RSV symptoms • Overall RSV symptoms 
Sustained resolution, assessed over entire study course, is defined as no evidence of recurrence once resolution has been reached and where:
 
 • Resolution is considered when All individual RSV concepts comprising relevant summary parameter are scored as 0 (none) or 1 (mild) for approximately 24h (as in the definition of time [hours] to resolution). • Recurrence identified if any of the individual RSV concepts comprising the RSV summary parameter scored >1 = 'not resolved' following previous resolution. 
Subjects will be evaluated over the course of the study and categorized ONCE as follows:
 
 • Not Resolved: if, over entire study course, individual RSV concepts comprising the RSV summary parameter have not resolved • Resolved With Recurrence: following resolution, individual RSV concepts comprising the RSV summary parameter >1 based on any of the subsequent ObsRO assessments • Resolved Without Recurrence: once resolved, individual RSV concepts comprising the RSV summary parameter maintained at 0 (none) or 1 (mild) based on subsequent ObsRO assessments

Measurement	Formula																																				
CLINICIAN PRESORS: ClinRO																																					
Clinically resolved status as based on PRESORS ClinRO: Day 1 to Day 8 [categorical]	
In hospitalized subjects: COHORT 1:
 
Day 1 to Day 8:
 
Clinically resolved status, is a composite endpoint per study day of assessment: Day 1 to Day 8 and reflects subject's worst situation on the study day of assessment.
 
A subject will be considered as clinically resolved on study day of assessment if, based on actual information collected, there is:
 
 • No oxygen supplementation • No supplemental hydration/feeding • No medical need of ICU 
AND
 
 • Resolution of key RSV symptoms based on PRESORS ClinRO ALL scored as 0 [none] or 1 [mild] on study day of assessment and considering the worst (highest) assessment collected on that day 
Since the PRESORS ClinRO is not assessed on a daily basis once a subject is discharged from the hospital (only assessed during follow-up visits to the site), imputation (based on the 'previous available-' and 'next available' PRESORS ClinRO assessment) will be applied if no PRESORS ClinRO available on a specific study day. Day 1 to Day 8 imputation is as follows:
 
  
 PREVIOUS Available PRESORS ClinRO	NEXT Available PRESORS ClinRO	Imputed Value	SENSITIVITY Analysis Imputed Value	
   
 Resolved	Resolved	Resolved	Resolved	
 
 Not resolved	Not resolved	Not resolved	Not resolved	
 
 Resolved	Not resolved	Not resolved	Not resolved	
 
 Not resolved	Resolved	Resolved	Not resolved	
 
 Resolved	Missing	Resolved	Resolved	
 
 Not resolved	Missing	Not resolved	Not resolved	
 
 Missing	Resolved	Resolved	Resolved	
 
 Missing	Not resolved	Not resolved	Not resolved	
  
	PREVIOUS Available PRESORS ClinRO	NEXT Available PRESORS ClinRO	Imputed Value	SENSITIVITY Analysis Imputed Value	Resolved	Resolved	Resolved	Resolved	Not resolved	Not resolved	Not resolved	Not resolved	Resolved	Not resolved	Not resolved	Not resolved	Not resolved	Resolved	Resolved	Not resolved	Resolved	Missing	Resolved	Resolved	Not resolved	Missing	Not resolved	Not resolved	Missing	Resolved	Resolved	Resolved	Missing	Not resolved	Not resolved	Not resolved
PREVIOUS Available PRESORS ClinRO	NEXT Available PRESORS ClinRO	Imputed Value	SENSITIVITY Analysis Imputed Value																																		
Resolved	Resolved	Resolved	Resolved																																		
Not resolved	Not resolved	Not resolved	Not resolved																																		
Resolved	Not resolved	Not resolved	Not resolved																																		
Not resolved	Resolved	Resolved	Not resolved																																		
Resolved	Missing	Resolved	Resolved																																		
Not resolved	Missing	Not resolved	Not resolved																																		
Missing	Resolved	Resolved	Resolved																																		
Missing	Not resolved	Not resolved	Not resolved																																		
Resolved status as based on PRESORS ClinRO: Day 1 to Day 8 [concepts]	
For ClinRO symptoms (concepts): activity level, sleep disturbance, retractions, tachypnea, breathing problems, feeding problems, cough, nasal secretions, wheezing, dehydration:
 
Day 1 to Day 8:
 
Resolved status per day will be categorized as:
 
 • RESOLVED: if individual RSV concept is scored as 0 (none) or 1 (mild) • NOT RESOLVED: if individual RSV concept is scored >1 • MISSING: if no ClinRO assessment for given day (no imputation) 																																				

Measurement	Formula
	
Note: resolved status will be derived for each study day considering the worst (highest) assessment collected per study day.

Resolved status BEFORE/ AFTER HOSPITAL DISCHARGE as based on PRESORS ClinRO [concepts]	
Hospital Discharge: In the subset of hospitalized subjects at time of hospital discharge: for each ClinRO concept, resolved status of the last ClinRO assessment BEFORE hospital discharge/first ClinRO assessment AFTER hospital discharge, will be categorized as described above.

Resolved status as based on PRESORS ClinRO: Day 1 to Day 8 [summary parameters]	
RSV summary parameters:
 
 • Key RSV symptoms • Overall RSV symptoms 
Day 1 to Day 8: Resolved status per day will be categorized as:
 
 • RESOLVED: if individual RSV concepts comprising the relevant summary parameter are all scored as 0 (none) or 1 (mild) • NOT RESOLVED: if any of the individual RSV concepts comprising the relevant summary parameter are scored >1 • MISSING: if no ClinRO assessment for given day (no imputation) 
Note: resolved status will be derived for each study day considering the worst (highest) assessment collected per study day.

Resolved status BEFORE/ AFTER HOSPITAL DISCHARGE as based on PRESORS ClinRO [summary parameters]	
RSV summary parameters:
 
 • Key RSV symptoms • Overall RSV symptoms 
Hospital Discharge: In hospitalized subjects at time of hospital discharge: for RSV summary parameters, resolved status of the last ClinRO assessment BEFORE hospital discharge/first ClinRO assessment AFTER hospital discharge, will be categorized as described above.

Time (hours) to resolution of RSV [summary parameter]: 12h supplementation free definition [time to event]	
For the summary parameter: key RSV symptoms considering ClinRO assessments during hospitalization only
 
In the subset of hospitalized subjects (Cohort 1), time (hours) from first dose of study drug until the date/time of first observed resolution of all individual RSV concepts comprising the relevant summary parameter (refer to Attachment 3 for concepts comprising each RSV summary parameter).
 
Where resolution is defined as:
 
 • All individual RSV concepts comprising relevant summary parameter are scored as 0 (none) or 1 (mild) • No oxygen- and/or hydration/feeding supplementation during previous 12 hours (as evaluated at the date/time of the ClinRO assessment)

Measurement	Formula						

Confirmed resolution is defined as:
 
 • A second consecutive timepoint before hospital discharge, indicating resolution as defined above OR • Hospital discharge within 24 hours after the last ClinRO assessment before hospital discharge indicating resolution (as defined above) 
This means that resolution can ONLY occur at the date/time of a ClinRO assessment. To illustrate:
 
Step1: check ClinRO assessment for resolution of RSV concepts comprising the summary parameter
 
Step 2: check if supplementation discontinued at least 12h prior to ClinRO assessment
 
Step 3: if YES to the above, subject considered resolved at timepoint. If NO, check next ClinRO assessment and repeat the aforementioned steps.
 
Step 4: check for confirmed response
 
In case individual RSV concepts comprising the relevant summary parameter are not resolved, data will be censored as follows:
 
  
 Situation	Censoring	
   
 Last record indicates resolution but insufficient recordings to meet the requirement of at least two consecutive assessments indicating resolution prior to hospital discharge and/or hospital discharge >24h after last assessment indicating resolution	Censored at date of last ClinRO assessment prior to hospital discharge	
 
 For subjects with missing data prior to hospital discharge (without previous resolution or evidence of hospital discharge) due to: 
 • Completion • Withdrawal/early discontinuation of the study • Lost to follow-up (LT FU) 	Censored at date/time of completion, withdrawal/discontinuation of the study or LTFU accordingly	
  
		Situation	Censoring	Last record indicates resolution but insufficient recordings to meet the requirement of at least two consecutive assessments indicating resolution prior to hospital discharge and/or hospital discharge >24h after last assessment indicating resolution	Censored at date of last ClinRO assessment prior to hospital discharge	For subjects with missing data prior to hospital discharge (without previous resolution or evidence of hospital discharge) due to: 
 • Completion • Withdrawal/early discontinuation of the study • Lost to follow-up (LT FU) 	Censored at date/time of completion, withdrawal/discontinuation of the study or LTFU accordingly
Situation	Censoring						
Last record indicates resolution but insufficient recordings to meet the requirement of at least two consecutive assessments indicating resolution prior to hospital discharge and/or hospital discharge >24h after last assessment indicating resolution	Censored at date of last ClinRO assessment prior to hospital discharge						
For subjects with missing data prior to hospital discharge (without previous resolution or evidence of hospital discharge) due to: 
 • Completion • Withdrawal/early discontinuation of the study • Lost to follow-up (LT FU) 	Censored at date/time of completion, withdrawal/discontinuation of the study or LTFU accordingly						

Measurement	Formula
	
Assessment at last ClinRO before hospital discharge does not indicate resolution:
 
Derive:
 
x = end date/time of supplementation + 12h
 
y = hospital discharge date/time
 
z = time slot:
 
 • 08:00 on the same day if the last ClinRO was a morning assessment (from 00:00 until 01:59) • 20:00 on the same day if the ClinRO was a morning assessment (from 02:00 until 13:59) • 8:00 the next day if the last ClinRO was an evening assessment (from 14:00 until 23:59)
	
Death (without previous resolution or hospital discharge)
 
Censored at date/time of death

time to event (hours) = (date/time of event or censoring – date/time of first dose of study drug)/3600, rounded to one decimal

OTHER CLINICAL COURSE ENDPOINTS

RSV-related complications: investigator assessment [protocol definition]	
Subjects who experienced a RSV-related complication after first dose of study drug will receive code 1, subjects who did not experience a complication will receive code 0.
 
The overall category will consist of any complication (answer to the question: "Is this AE a complication related to the current respiratory infection?").
 
The following subcategories will also be analyzed:
 
 ▪ Respiratory complications, including 
 ○ Bacterial complications ○ Viral complications ▪ Non-respiratory infectious complications, including 
 ○ Bacterial complications ○ Viral complications ▪ Other 
The RSV-related complication as per original definition will be provided as needed.

RSV-related complications: modified definition	Any subject who experienced at least one emergent adverse event included in the list of complications below will receive code 1, subjects who did not experience any of the specified emergent adverse events will receive code 0.

Measurement	Formula
[study physician-identified complications]	
 Respiratory complications: respiratory failure, respiratory distress, apneic attacks, bronchiolitis, bronchial obstruction, pneumonia, asthmatic crisis. Infectious complications: otitis media, bacterial respiratory tract infections, sepsis; Cardiovascular complications: arrhythmia, cardiogenic shock, hemodynamic instability, congestive cardiac failure; Acid-base or electrolyte complications: metabolic acidosis (serum $\text{HCO}_3^- < 16$), metabolic alkalosis (serum $\text{HCO}_3^- > 30$) 
The final list of emergent adverse events to be considered as per modified definition of RSV-related complications, will be reviewed and documented prior to a database lock.
 
The modified definition for RSV-related complications will primarily be used as follows:
 
 from IA#3 and onwards in any decision rule that requires RSV-related complications data
Need for antibiotics related to complications associated with RSV: Investigator assessment [categorical]	
Need for antibiotics is defined as 'Yes' if the answers to the following 2 questions on the Adverse Events eCRF are answered with 'Yes' (Yes to both questions):
 
 Is this AE a complication related to the current respiratory infection? Concomitant or additional therapy given for this adverse event? 
And if the answer to the following question on the Concomitant Medications eCRF for the related medication is answered with 'Yes'.
 
 Was this medication an Antibiotic?

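### Time from discharge to symptom resolution (Table 22) is derived from the child's first-ever resolution, and its 0 h rule contradicts its stated population

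*SAP*

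**What the plan says.** The row in SAP Section 5.4.1, Table 22, covers key and overall RSV symptoms as rated by the caregiver (ObsRO).

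- **Population:** "In the subset of hospitalized subjects (Cohort 1) ‘not resolved’ at date/time of hospital discharge".
- **Quantity in words:** hours from discharge to the first observed resolution, meaning all component symptoms scored 0 or 1 for about 24 h.
- **Source variables:** "Utilizing the same derived variables as detailed in Section 5.3.1.2.1", namely time to resolution and time to hospital discharge.
- **Formula:** it opens "max(time to resolution [as defined above" and in full reads "max(time to resolution [as defined above]) – time to hospital discharge), rounded to one decimal".
- **Zero rule:** for children resolved at discharge, "time (hours) is set to 0h".

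Table 17 (Section 5.3.1.2.1) defines the re-used time to resolution as running from first dose to the first resolution, wherever it occurs. Time to discharge is defined in Table 20 (Section 5.3.1.3.2), not in the section that the row cites.

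Section 5.4.2 sends the endpoint to Kaplan-Meier and to an AFT model like that of Section 5.3.2.2, which is log-logistic, with both curves overlaid on one plot. Section 5.5 correlates the key-symptom version with the antiviral endpoints in Cohort 1.

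The endpoint list in Section 5.4 has "Time (hours) to resolution of key- and overall RSV summary parameters from hospital discharge (ObsRO" with a supplementation-free label. The Table 22 row states no such criterion.

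**The concern.** The words and the formula describe different quantities. The words start the clock at discharge. The formula takes a resolution that may have happened in hospital and subtracts the discharge time. The two agree only if the first-ever resolution falls after discharge, and the row imposes no such condition. The SAP itself provides for relapse: the sustained-resolution row of Table 22 has a category defined by "following resolution, individual RSV concepts comprising the RSV summary parameter >1 based on any of the subsequent ObsRO assessments".

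The population and the zero rule also conflict. One sentence restricts the endpoint to unresolved children and another assigns values to the resolved ones. With or without the zeros, the endpoint answers a different question and has a different median.

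A programmer would have to choose among readings that give different results. In the Section 5.5 rank correlation, a negative value would place a relapsing child ahead of children who were resolved at discharge.

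**Working it through.** The SAP gives no figure for this endpoint, so there is none to reproduce. The check applies the printed rule to a constructed child and then looks at the zeros.

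**1. A child who relapses before discharge.** Twice-daily entries, with the Table 17 requirement of three consecutive resolved recordings:

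- resolved at 24, 36 and 48 h after first dose
- unresolved at 60 and 72 h
- discharged at 74 h
- resolved again from 84 h onwards

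The first-ever resolution is at 24 h. The time that the row describes is 84 − 74 = **+10 h**.

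| Reading of the formula | Value |
|---|---|
| As printed (maximum of one argument) | 24 − 74 = −50 h |
| Maximum over symptoms, e.g. 24 h and 36 h (Table 20 takes maxima over components) | 36 − 74 = −38 h |
| Floor at zero | max(0, −50) = 0 h |
| Latest resolution episode | 84 − 74 = +10 h |

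Only the last reading gives the described value here, and Section 5.3.1.2.1 derives no such variable.

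**2. A child censored before discharge.** Suppose first dose is at 08:00 and the last diary entry is an unresolved morning entry at 48 h. Table 17 censors at 20:00 that day, which is 60 h. With discharge at 74 h the censoring time is 60 − 74 = **−14 h**.

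**3. The zeros in the two analyses.** Kaplan-Meier can hold an event at 0 h. A log-logistic AFT model works on log time, and zero or negative times have no finite logarithm, so they cannot enter its likelihood as events. The two overlaid curves would then cover different children.

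**4. What the zeros do to the median.** If a share q is set to 0 h, the pooled median solves q + (1 − q)F(t) = 0.5, where F is the distribution in unresolved children. The SAP gives neither q nor F, so every input below is an assumption.

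- Exponential, median 72 h: t = 72 × log2(2(1 − q)). For q = 10, 20, 30 and 40% this gives 61.1, 48.8, 35.0 and 18.9 h.
- Log-logistic, median 48 h, q = 30%: F = 0.2/0.7 = 0.286 and odds = 0.4. With scale 0.65, 48 × 0.4^0.65 is about 26 h. With scale 1/0.65 (the scale value in Section 1.4), it is about 12 h.
- At q of 50% or more the median is 0 h in every case.

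**5. The supplementation criterion.**

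- Section 5.4 list: labelled supplementation-free.
- Table 22 row: symptom scores only, pointing to a section with no supplementation criterion.
- Section 5.4.2 heading: names this endpoint apart from the supplementation-free ones.
- Section 5.5: attaches the supplementation-free label to ordinary time to resolution but not to this endpoint.

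**The case against.** The strongest defence is that the formula is visibly malformed and the words already state the right quantity. If being resolved at discharge is judged from the same derived variable (a 24 h resolution reached by then or not), every event among the unresolved falls after discharge and no negative event time arises. The relapsing child simply takes the 0 h branch. A floor at zero does the same.

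So negative times are one reading, not a certainty; that part of the defence stands. It does not rescue the rule, because on either reading a child with symptoms at discharge scores 0 h and the later recovery at home is lost.

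Three further points stand:

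- The recurrence category covers the whole study and carries no rate. It does not show how often a child resolves for about 24 h in hospital, relapses and is discharged unresolved.
- Assigning 0 h is a convention used elsewhere in the SAP (Table 20), so the zeros may be meant to complete the derivation for the rest of Cohort 1. The wording still contradicts the stated population.
- Deleting the zeros has a cost. It compares arms within a subset selected after randomisation, on a state that treatment may affect.

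**Conclusion.** The row needs correcting. It derives a different quantity from the one it describes, and its population and zero rule disagree. The zero conflict needs no relapse to matter; the misdating needs either a relapse before discharge or censoring before discharge. The error in a single child can be large (−50 h or 0 h against +10 h in the constructed case). The number of children affected is unknown, and the pooled medians above only illustrate the direction under assumed inputs.

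Several stronger conclusions that a reader might draw are not supported:

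- **Negative times are certain.** They depend on how the malformed expression and the discharge status are read.
- **Known recovery times are lost for every child with a negative value.** This holds for relapsing children who later resolve. For a child censored before discharge the true time is unknown.
- **The zeros must be removed.** Either population is defensible if it is stated and handled consistently.
- **The supplementation criterion should be added.** Section 5.4 says so, but Table 22, Section 5.4.2 and Section 5.5 lean the other way.
- **The main results are at risk.** This is an exploratory Cohort 1 endpoint, analysed mainly in children with symptom onset within 3 days. Beyond its own analyses it touches only the Section 5.5 correlation. The primary endpoint, key clinical endpoints and interim rules do not use it.

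**What to change.** Rewrite the Table 22 row:

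1. Start the clock at first discharge, and define the event as the first approximately 24 h resolution that starts at or after discharge.
2. Define resolved at discharge explicitly, for example by the last ObsRO entry before discharge.
3. Apply the Table 17 censoring rules to the period after discharge, so that no censoring time is negative.
4. Make the population and the zero rule agree, in one of two ways:
   - Limit the endpoint to unresolved children, drop the 0 h sentence, report the proportion resolved at discharge by arm, and note that this is a post-randomisation subset.
   - Include all Cohort 1 children and state how zeros are handled in the AFT model, so that it and Kaplan-Meier cover the same children.
5. State whether the supplementation criterion applies, and align Sections 5.4, 5.4.1, 5.4.2 and 5.5.
6. Replace the formula and correct the cross-reference for time to discharge to Section 5.3.1.3.2.

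The cost is SAP wording and a re-derivation from diary and discharge data already collected.
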